5.1.1.2 Protocol Deviations

Protocol deviations are specified in Appendix 1 (Section 6.1.2).

All protocol deviations will be reviewed at the Data Cleaning Meetings (DCM) and decisions made on whether they should be considered important or not.

Important protocol deviations (IPDs) are deviations from the protocol which could potentially have a meaningful impact on study conduct or on either the primary or key secondary outcome(s) for an individual study participant. The criteria for identifying such protocol deviations will be defined within the IPD specifications document.

Important protocol deviations will be categorized as follows:

1. Inclusion/exclusion criteria deviations
2. Incorrect treatment or dose administered
3. Procedural non-compliance
4. Prohibited concomitant medication use
5. Withdrawal criteria deviation

All IPDs will be reviewed as part of the ongoing data cleaning process and data evaluation. At least one Data Evaluation Meeting (DEM) will be performed prior to the final database lock after all data have been verified/coded/entered into the database to discuss exclusion of study participants from analysis populations.

Participants may be excluded from the safety set if they do not pass the inclusion/exclusion criteria. However, should a participant be mistakenly dosed despite failing the inclusion/exclusion criteria, then their safety data would need to be reported as part of the safety analysis. Participants may be excluded from other analysis sets, but this will be determined on a case-by-case basis. If the deviation is deemed to have the potential to bias the analyses for the duration of the study then the whole participant may be removed in a sensitivity analysis on the key endpoints. The removal of the participant and the rationale will be clearly documented within the relevant TFLs.

Important protocol deviations will be identified and classified by the deviation types in the IPD document. A listing of all IPDs identified at the DCMs will be presented for all participants based on the safety set and will include the deviation type and description.

The IPDs will be tabulated using the SS and will present the deviation type and description by treatment group.

5.1.1.3 Treatment assignment and treatment groups

It is expected that participants will receive treatment as randomized; hence safety analyses will be based on the SS-as randomized. However, if it is determined that participants received treatment other than what they were randomized to, then for PK and safety analyses purposes participants will be allocated to the actual treatment they received (SS-as treated).

5.1.1.4 Definition of Analysis by Variables

Analysis of study parameters and corresponding to be tabulated by variables are defined in below [Table 6](#) and [Table 7](#)

Table 6 Definition of Analysis by Variables

Term	Variables
Sequence	Sequence 1 (ABC)
	Sequence 2 (BCA)
	Sequence 3 (CAB)
	Sequence 4 (ACB)
	Sequence 5 (BAC)
	Sequence 6 (CBA)
Formulation and feeding conditions	A: Granules in capsule █ (fasted condition)
	B: Tablet formulation █ (fasted condition)
	C: Tablet formulation █ (fed condition)

Note: A: Granules in capsule (fasting); B: Tablet formulation (fasting); C: Tablet formulation (fed).

Table 7 Analysis to be performed by variables

Analysis	Variable
Disposition	Sequence
Medical History	
Concomitant Medications	
Important Protocol Deviations	
PK Concentration	Formulation and feeding condition
Adverse Events	Formulation and feeding condition
Laboratory Values	Time Point and Sequence

Analysis	Variable
Vital Signs	
ECG	

5.1.1.5 Center pooling strategy

This is a single center study.

5.1.1.6 Coding dictionaries

Medical history and adverse events (AEs) will be coded using the current version of Medical Dictionary for Regulatory Activities (MedDRA) at time of database lock. Medications will be coded using the current version of World Health Organization Drug Reference List (WHO-DRL) at time of database lock. Medical procedures will not be coded.

5.1.1.7 Handling of repeated and unscheduled measurements

All repeated and unscheduled measurements will be presented in the data listings, where applicable. Repeated measurements are defined as more than 1 measurement at same time point. The following general rules will apply to all repeated and unscheduled measurements:

- For repeated measurements obtained prior to the first dose of study medication the latest value (which may be scheduled or unscheduled) will be used in the calculation of the descriptive statistics.
- For repeated measurements obtained for the designated Baseline value, the latest value (which may be scheduled or unscheduled) will be defined as the Baseline provided that this occurred prior to the first dose of study medication.
- Unscheduled measurements and repeated measurements after the first one at a given time point will not be used in the descriptive statistics at time points after first dose of study medication.
- Unscheduled measurements performed for the Early EOS/WD visit will be assigned to the EOS Visit and analyzed accordingly as an EOS Visit.

5.2 Participant Dispositions

Participant screening and primary reason for screen failure will be summarized using the ASPS. The summaries will include the following:

- Number of participants screened
- Number and proportion of participants rescreened
- Number and proportion of participants with screen failures (Not counting successfully rescreened participants)
- Number and proportion of screen failures by primary reason for screen failure (Based on the later screening visit)

By-participant listings of rescreened participants will be presented using the ASPS.

Participant disposition will be summarized using the ASPS. Each summary will include the following:

- Date of first screening visit
- Date of last visit for last participant
- Number of participants screened
- Number of participants in each analysis set, by treatment sequence (according to randomized treatment).

Disposition of analysis sets will be tabulated using the ASPS. Each table will present the total number of participants in the ASPS, as well as the number and percentage of participants in each analysis set by treatment sequence.

Study completion/discontinuation and primary reason for discontinuation will be summarized using the RS. Each table will present the following, by treatment sequence:

- Number and percentage of participants that started the study
- Number and percentage of participants completing the study
- Number and percentage of participants discontinuing the study
- Number and percentage of participants discontinuing the study by primary reason for discontinuation.

Participants that started the study are defined as participants that were randomized. Participants completing the study are those participants completing the SFU visit AND who did not discontinue dosing or withdraw from the study for any reason before the SFU.

Study discontinuation due to AEs will be tabulated using the RS. Table will present the number and percentage of participants who discontinued the study due to AE by treatment sequence.

By-participant listings of participant who did not meet study eligibility criteria will be presented by treatment sequence, using the ASPS. The listing will include inclusion criteria that were not met and the exclusion criteria that were met.

By-participant listings of participant disposition will be provided using the ASPS by treatment sequence. The listings will include:

- Study termination/completion status
- Date of informed consent
- Date of randomization
- Date and time of first study treatment (first start date and time)
- Date and time of last study treatment (last stop date and time)
- Date of last contact
- Date of premature study termination for successfully screened participants dropping out of the study.

- Date of screen failure for screen failure participants (based on the last screening visit in case of rescreen)
- Primary reason for premature study termination
- Primary reason for screen failure (Based on the last screening visit in case of rescreen)

By-participant listings of participant inclusion in each analysis set will be presented by sequence, using the ASPS.

By-participant listings of study discontinuation will be presented by sequence, using the RS.

5.3 Pharmacokinetics

Unless otherwise stated, PK analysis will be performed on the PKS.

5.3.1 Analysis of Concentration Measures

The plasma concentration-time profiles will be summarized by formulation and feeding condition, using descriptive statistics (number of available observations, arithmetic mean, sd, geometric mean, geometric coefficient of variation (geometric cv), median, IQR, minimum, and maximum).

Individual concentration-time profiles will be displayed graphically on a linear-linear scale and semilogarithmic scale. Individual concentration-time profiles for a given formulation and feeding condition will be presented on the same plot.

Overall geometric mean plasma concentrations-time curves and corresponding 95% CIs will be displayed by formulation and feeding condition.

Individual concentrations will be listed by formulation and feeding condition.

Standard reporting procedures of individual values and descriptive statistics for plasma concentration data in listings, tables, and figures are described in Appendix 2 (Section [6.2.1](#)).

5.3.2 Pharmacokinetic Parameters

The following PK parameters will be determined using the actual recorded sampling times and non-compartmental method(s) with Phoenix WinNonlin® (Version 8 or higher), as applicable using Guideline on performing NCA analysis (2017) : C_{\max} , t_{\max} , AUC_{0-t} , AUC , $AUC\%Extrap$, $t_{1/2}$, Lambda z (λ_z), CL/F (Minzasolmin only), Vz/F (Minzasolmin only), MRC_{\max} , and $MRAUC$ from the plasma concentration-time data.

Table 8 Non-compartmental PK parameters for Minzasolmin in plasma

PK Parameter	Definition
AUC	The AUC from time zero to infinity (mass * time * volume ⁻¹).
AUC _{0-t}	The AUC from time zero to the last measurable drug concentration sampling time (t _{last}) (mass * time * volume ⁻¹).
C _{max}	The maximum (peak) observed drug concentration following a single dose administration (mass * volume ⁻¹).
t _{max}	The time to reach maximum (peak) drug concentration following a single dose administration (time).
t _{1/2}	The elimination half-life associated with the terminal slope (λ_z) of a semilogarithmic concentration-time curve (time).
CL/F ^a	The total apparent body clearance of drug (volume/time).
Vz/F ^a	The apparent volume of distribution during terminal phase (associated with λ_z) (volume).
Lambda_z (λ_z)	Terminal elimination rate constant (1/time).
AUC%Extrap ^b	Area under the <matrix> concentration-time curve extrapolated from the time t to infinity as a percentage of total AUC.
Rsq_adj ^c	Square of the correlation coefficient (adjusted for the number of data points included) associated with λ_z .
MRC _{max} ^d	C _{max} metabolite to parent ratio.
MRAUC ^d	AUC from time zero to infinity metabolite to parent ratio.

^a For Minzasolmin only^b AUC%Extrap is listed if AUC is presented^c Rsq_adj is listed only^d Metabolites only

PK parameters of Minzasolmin will be listed and summarized using descriptive statistics similarly to the plasma concentrations. Additionally, the PK parameters will be presented via boxplot by formulation and feeding condition. GeoMean ratio and 90%CI of primary PK parameters obtained from mixed model will be presented via forest plot.

Standard reporting procedures of individual values and descriptive statistics for PK parameters in listings, tables, and figures are described in Appendix 2 (Section 6.2.2).

5.4 PK Endpoints Analysis

5.4.1 Definition of endpoint(s)

PK endpoints are based on the definitions in Table 8.

The primary endpoints for PK objectives in both parts are:

- AUC_{0-t}
- AUC
- C_{max}

The other PK endpoints are defined as follows:

- For minzasolmin:
 - t_{max} , $t_{1/2}$, CL/F, and Vz/F (if possible but not limited)
- For [REDACTED] metabolites:
 - C_{max} , t_{max} , AUC_{0-t} , and AUC in fasting and fed conditions
 - metabolite/parent C_{max} and AUC ratio, as appropriate.
 -

5.4.1.1 Analyses required for the Primary Objective (on Primary PK endpoints)

The primary comparisons of interest are:

- New tablet vs ‘granules in capsule’ under fasted condition (B vs A)
- New tablet formulation under fasted condition vs under fed condition (B vs C)

To estimate these comparisons, the primary analysis model will be applied to the 2 sets of data separately: namely, all data under fasted condition (B vs A comparison) and all data for the new tablet formulation (B vs C comparison).

The PK parameters C_{max} , AUC_{0-t} , and AUC will be estimated using analysis of variance (ANOVA), adapted to crossover designs. The model will include a random intercept term for participant within sequence and fixed effect categorial terms for sequence, period, and Treatment condition? (3 formulation x feeding conditions).

The dependent variables will be logarithmically transformed by natural logarithms (\ln) prior to statistical testing, following the usual recommendations.

The linear mixed model is given as following:

$$\ln(Y) = Q + S_i + P + T + \varepsilon, \text{ where} \quad (1)$$

- $\ln(Y)$ is the log transformed PK parameter value,
- Q is the fixed effect term for the sequence,
- P is the fixed effect term for the period,
- T is the fixed effect term for the treatment condition,
- S_i is the random effect term of the participant nested to the sequence,
- ε is the random error.

The PROC MIXED procedure in the Statistical Analysis Software (SAS) will be used for this analysis. For estimation based on a linear mixed model, covariance matrix applied to the within-subject error will be estimated by restricted maximum likelihood (REML). The Kenward-Roger approximation will be used to estimate the degree of freedom. Variance component structure will be used for the variance-covariance matrix for this linear mixed model.

For each PK parameter the least square mean (LSMEAN) and corresponding 95% confidence interval (CI) for each Treatment condition, the difference in LSMEANs between Treatment conditions, and corresponding 90% CI will be calculated. These values will then be back-transformed to give the estimate of the geometric mean ratio (GMR) for each Treatment condition comparison alongside with their corresponding 90% CI.

The estimates of the geometric mean ratios with their corresponding 90% CI will be displayed in a summary plot. Additionally, the within-participant CVs will be calculated based on the within-participant estimate of variance obtained from each ANOVA model. Please check [Table 12](#) at Appendix 3 for model specifications.

5.4.1.2 Sensitivity analysis required for Primary Objective (on Primary PK endpoints)

The comparisons of interest described in [Section 5.4.1.1](#) will be assessed for each PK parameters by applying a mixed model procedure to all trial data. Please check [Table 1](#)[Table 12](#) at appendix 3 for sensitivity analysis model specifications.

5.4.1.3 Analyses required for Other Objective (on Other PK endpoints)

The other PK parameters of Minzasolmin and metabolites will be summarized by formulation and feeding condition using descriptive statistics as described in [Section 5.3.1](#).

- For Minzasolmin: t_{max} , $t_{1/2}$, CL/F , and Vz/F (if possible but not limited). For t_{max} , only the median, IQR, minimum, and maximum will be reported.
- For [REDACTED] metabolites: C_{max} , t_{max} , AUC_{0-t} , AUC , and each metabolite/parent C_{max} and AUC ratio (corrected for the molecular weight of the entities), as appropriate.

$$MR_C_{max} = \frac{C_{max}(\text{metabolite})}{C_{max}(\text{parent})} * \frac{\text{Molecular weight (parent)}}{\text{Molecular weight (metabolite)}}$$

$$MR_AUC = \frac{AUC(\text{metabolite})}{AUC(\text{parent})} * \frac{\text{Molecular weight (parent)}}{\text{Molecular weight (metabolite)}}$$

where,

Molecular weight (parent) = 425.59 g/mol

Molecular weight [REDACTED]

Molecular weight [REDACTED]

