Minzasolmin has not been approved by any health authorities worldwide as of the date of this document. UCB has conducted 5 Phase 1 clinical studies to support the development of minzasolmin. The pharmacokinetics (PK) of minzasolmin has been well characterized following administration of single and multiple doses in healthy volunteers and patients with PD (UP0030, UP0023, TM0017, UP0077, UP0078). Minzasolmin is rapidly absorbed following administration of single (███████ or multiple doses (███████) with maximum plasma concentration were attained within 1.5 to 2 hours and had moderate to extensive tissue

distribution. The apparent terminal elimination half-life ($t_{1/2}$) of minzasolmin at single doses of [REDACTED] has been found to be approximately 11 to 13 hours. In general, the maximum observed plasma concentration (C_{max}) and area under the plasma concentration-time curve from time zero to infinity (AUC) increased in an approximately dose-proportional manner after a single dose ([REDACTED]) and multiple doses ([REDACTED]). In the dose range evaluated, minzasolmin follows linear kinetics (no change in apparent total body clearance [CL/F] and apparent volume of distribution [Vz/F] was observed), and steady state was achieved by Day 7 following multiple dose administration. The PK of minzasolmin were also comparable between healthy volunteers and patients with PD (UP0030 and UP0077). Minzasolmin had an acceptable safety and tolerability profile (UP0023, UP0030, TM0017, and UP0077).

The effect of food has been evaluated with granules in capsule in the previous study UP0078. Food intake delays gastric emptying as expected thereby increasing t_{max} (1.5 hour to 3 hour). The rate and extent of minzasolmin absorption (C_{max} and AUC, respectively) were not impacted by food. The point estimates for the geometric least squares mean ratio of fed/fasting calculated for minzasolmin C_{max} and AUC were 104.5% and 109.4%, respectively. The elimination rates were similar between the fed and fasting groups for minzasolmin and its metabolites.

Minzasolmin is currently being tested in an ongoing Phase 2a study (PD0053), its extension study (PD0055), and an ongoing Phase 1 study (UP0073). Further information regarding UP0023, UP0030, TM0017, UP0077, and UP0078 is provided in the Investigator's Brochure (IB).

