4.2 Scientific rationale for study design

A new tablet formulation is developed for minzasolmin, which is planned to be used in future studies and for commercialization purpose. The current study UP0152 is designed to evaluate the relative bioavailability of a new tablet formulation compared with the current clinical formulation (ie, granules in capsule) under fasting condition. In addition, the study is also designed to evaluate the potential effect of a high-fat meal on the PK of minzasolmin when administered as tablet formulation. A crossover study design was selected as it provides more robust comparison between different formulations and fed conditions as each participant will receive all study treatments. Six sequences were implemented in order to balance the allocation of treatments across study periods.

The half-life of minzasolmin and its 2 metabolites (████████) are 11, 10 and 16 hours, respectively (see the IB for further details). Considering 5 half-lives for elimination of the drug, the 4 days washout is considered adequate for the study. In study UP0073, a similar design and washout period was used, and carryover (<5% of C_{max}) was observed in only few participants. The t_{max} for minzasolmin and the ██████████ metabolites were 1.5, 2.0, and 2.0 hours, respectively (see the IB for further details).

UP0152 will provide safety, tolerability, and PK information of minzasolmin formulations in fed condition (tablet formulation) and fasting condition (tablet and ‘granules in capsule’ formulation) after single oral doses of minzasolmin ██████████ administered once per period in healthy study participants.

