9.2.3 Other PK endpoint analysis

The other PK parameters of minzasolmin and metabolites will be summarized by formulation and feeding condition (fed vs fasting) using descriptive statistics as below:

- For minzasolmin: t_{max} , $t_{1/2}$, CL/F, and Vz/F (if possible but not limited). For t_{max} , only the median, minimum, and maximum will be reported.
- For [REDACTED] metabolites: C_{max} , t_{max} , AUC_{0-t} , AUC, and each metabolite/parent C_{max} and AUC ratio (corrected for the molecular weight of the entities), as appropriate.
- Additional analyses of PK parameters might be conducted as appropriate.

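### tmax is the parameter with a documented food effect, yet the plan gives it no within-participant contrast and no interval

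*SAP*

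**What the plan says.** - **tmax summaries.** SAP 5.4.1.3 states that for tmax "only the median, IQR, minimum, and maximum will be reported", by formulation and feeding condition. Protocol 9.2.3 and SAP 6.2.2 give a shorter list: "only the median, minimum, and maximum will be reported". The two SAP sections therefore disagree on the IQR.
- **Other displays.** SAP 5.3.2 has individual values listed and adds a plot: "Additionally, the PK parameters will be presented via boxplot by formulation and feeding condition".
- **Models and intervals.** The mixed models and the 90% CIs for ratios (SAP 5.4.1.1, 5.4.1.2 and Table 12) cover AUC0-t, AUC and Cmax only.
- **Open door.** Protocol 9.2.3 allows more: "Additional analyses of PK parameters might be conducted as appropriate". No tmax contrast is specified under it.
- **Prior food data.** Protocol 2.2: "The effect of food has been evaluated with granules in capsule in the previous study UP0078". There, "Food intake delays gastric emptying as expected thereby increasing" tmax from 1.5 h to 3 h. The fed/fasting ratios were 104.5% for Cmax and 109.4% for AUC, and the protocol reads both as unaffected.
- **Design.** Protocol 4.2 chose a crossover because "it provides more robust comparison between different formulations and fed conditions as each participant will receive all study treatments".
- **Grid.** Samples are taken predose and at 0.5, 1, 1.5, 2, 4, 8, 12, 24, 36, 48, 72 and 96 h (Protocol 1.3, footnote h).

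**The concern.** The study asks what food does to the PK of the tablet. In the documents' only earlier food data, the visible change was in tmax. For that parameter the reader of the report gets two columns of descriptive statistics and has to subtract one median from the other.

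The subtraction has two weaknesses. It carries no interval, so nothing in the planned output shows how far an observed delay could be chance. It is also coarse: a delayed tmax near 3 h falls where no sample is taken, so the fed median tends to land on 2 h or 4 h. The same trial could report a delay of about half an hour or about two and a half hours. Each participant has both periods, so a steadier estimate with an interval can be had from data already collected.

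**Working it through.** **1. Is there a planned figure to reproduce?** Not for tmax: the documents give no SD, within-participant correlation or precision for it. The stated power figures concern AUC0-t. They reproduce at an implied CV of 14.7% (85.0%, 91.9% and 95.8% for 12, 15 and 18 completers at a ratio of 0.95) but do not bear on this point.

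**2. What values can the subtraction take?** With 18 participants the median is the mean of the 9th and 10th ordered values. If fed values cluster at 2 h and 4 h, the fed median at nominal times is 2, 3 or 4 h. Against a fasting median of 1.5 h, the difference is:
- 2 - 1.5 = 0.5 h
- 3 - 1.5 = 1.5 h
- 4 - 1.5 = 2.5 h

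**3. Sampling gap or lost pairing?** Simulation with n = 18, lognormal tmax with medians 1.5 h and 3 h (UP0078), assumed log-SD 0.4 or 0.6, assumed within-participant correlation 0 or 0.75, and 4000 trials per row. tmax was either left continuous or moved to the nearest planned time on the log scale. Entries are the SD in hours of the difference of medians, then of the paired Hodges-Lehmann estimate (the median of all pairwise averages of the within-participant differences).

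| log-SD | correlation | continuous tmax | planned grid | SD ratio on grid |
|---|---|---|---|---|
| 0.4 | 0 | 0.388 / 0.345 | 0.842 / 0.386 | 2.18 |
| 0.4 | 0.75 | 0.288 / 0.224 | 0.794 / 0.298 | 2.67 |
| 0.6 | 0 | 0.585 / 0.539 | 0.916 / 0.605 | 1.51 |
| 0.6 | 0.75 | 0.434 / 0.360 | 0.797 / 0.427 | 1.87 |

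With continuous tmax the two estimates differ little (0.388/0.345 = 1.12 in the first row). On the grid the gap is large even at zero correlation. Most of the loss is therefore the median jumping across the unsampled 2-4 h interval.

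**4. A more realistic model.** One-compartment profiles with half-life 11 h (Protocol 4.2), CV of tmax 30-50%, 5-10% noise per sample, correlation 0-0.75, tmax read from the planned grid. All but the half-life, the medians and the grid are assumptions.
- 18 participants, true shift 1.5 h to 3 h: SD 0.81-0.92 h for the difference of medians, 0.32-0.56 h for Hodges-Lehmann. One zero-correlation case gives 0.83 against 0.35 h.
- At correlation 0.5, the difference of medians reads 0.5 h or less in 20-32% of trials and 2.5 h or more in 28-46%. Hodges-Lehmann does so in 1-6% and 1-5%.
- 12 participants, with log-SD 0.3-0.5 as the assumed spread: 0.81-0.93 h against 0.40-0.72 h.
- 18 participants, no true shift: 0.23-0.31 h against 0.16-0.30 h.

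**5. Can the interval be formed?** With n participants there are n(n+1)/2 pairwise averages, counting each difference with itself. From the exact signed-rank distribution without ties:
- n = 18: 18 x 19 / 2 = 171; limits are the 48th and 124th ordered values, coverage 90.1%.
- n = 12: 12 x 13 / 2 = 78; limits are the 18th and 61st, coverage 90.8%.

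**6. Period effects.** With period effects p1, p2, p3, the difference C-B carries p3-p2 (ABC), p2-p1 (BCA), p1-p3 (CAB), p2-p3 (ACB), p3-p1 (BAC) and p1-p2 (CBA). These sum to zero, and so do the six terms for B-A. Raw differences are thus balanced for additive period effects on average if sequence sizes stay equal, and nearly so if a few participants drop out.

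**The case against.** The best defence is that tmax is an 'Other' endpoint. The primary objective is tied to AUC0-t, AUC and Cmax, no hypothesis, margin or power statement uses tmax, and Protocol 2.2 treats Cmax as its measure of absorption rate. Cmax gets a model and a 90% CI for both contrasts. Descriptive reporting fits that status, and the listings let anyone compute the paired differences. This stands as a limit on the weight of the point. It does not supply an interval, and permission for additional analyses is not a specification; a contrast written down beforehand is worth more than one chosen after open-label data are seen.

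Four stronger readings are tempting, and the documents do not support them:
- *The plan discards the crossover pairing and so halves precision.* The pairs stay in the data, and step 3 shows that the grid causes most of the loss. For means, ignoring pairing inflates the variance by 1/(1 - correlation): 1.0 at 0, 2.0 at 0.5, 4.0 at 0.75. The documents give no correlation for tmax, so no fixed figure such as one half follows.
- *Only medians are reported.* Minimum, maximum, boxplots, listings and, in one section, the IQR are planned too.
- *tmax will show a food or formulation effect for the tablet.* The 1.5 h to 3 h shift is a capsule result and says nothing about tablet against capsule.
- *The trial cannot assess a tmax shift.* It can; the analysis is just not prespecified.

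The remedy also has limits. Ties on the grid make the interval approximate, the gap between 2 h and 4 h remains, and raw differences are not adjusted for period.

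**Conclusion.** The point holds as a modest reporting gap. No within-participant tmax contrast and no interval is prespecified, although tmax is the parameter for which the documents report a food effect. If the tablet behaves as the capsule did, the difference of condition medians with 18 participants has an SD of about 0.8-0.9 h, against about 0.3-0.6 h for the paired Hodges-Lehmann estimate. This rests on assumed CV 30-50%, sample noise 5-10%, correlation 0-0.75 and a fed tmax centred in the sampling gap. Without a shift the advantage is small. The primary PK conclusions are untouched. The disagreement between SAP 5.4.1.3 and 6.2.2 on the IQR is a separate, certain inconsistency.

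**What to change.** In SAP 5.4.1.3 and 6.2.2, for minzasolmin tmax in PKS participants with both relevant periods, add the Hodges-Lehmann median of the within-participant differences C-B (food) and B-A (formulation), each with a signed-rank 90% CI. Use actual sampling times, label the results descriptive, attach no test or margin, and state that ties make the interval approximate and that period is not adjusted for. Keep the per-condition statistics, and give the same list (IQR or not) in both sections. Record the addition in SAP 6.4, since Protocol 9.2.3 lists only per-condition statistics.

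Cost: a few lines of SAP text and one small table from data already collected. No extra sample, visit or participant is needed.
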